6.2 Procedures for Informed Consent

If a potential participant contacts, or is referred to the research team, an appointment will be set up to complete the informed consent process and pre screening checklist. During this meeting, a research team member with TCPS-2 training, other than [name], will go through the information letter and consent form (attached, Section 16.2) with the potential participant. The potential participant will be given at least 24 hours to consider volunteering for the study, as well as ask any questions they may have regarding the study. Potential participants are welcome to contact another member of the research team or any of the listed Research Ethics Boards to ask such questions prior to signing the consent form. If the potential participant wishes to consent to the study, they will indicate this by signing the consent form (attached, 16.3) and providing it to a research team member. The participant will be given a copy of the consent form to take home. The original will be retained by the research team as part of the study file.

6.3 Procedures for Participant Screening

Once informed consent is obtained, a trained member of the research team will determine the potential participant's eligibility using the screening checklist (attached, Section 16.3). If the potential participant meets these criteria, they will be included in the study and given a participant code number. If the potential participant does not meet these criteria, their signed consent form as well as the screening checklist and will be marked as a screen-fail and kept in a "Screen-Fail" binder in a locked filing cabinet in a secure office to be kept for a minimum of five years.

6.4 Procedures for Participant Enrolment /Allocation /Randomization

To achieve adequate enrolment, recruitment flyers will be placed at several locations and clinics around Thunder Bay. Once informed consent has been obtained, and the potential participant has been deemed eligible through the screening process, age and sex of the participant will be used to randomly assign the participant to an intervention group through a process called minimization. This process ensures group sizes are equal and eliminates potential bias that may be introduced which is important for clinical research of small sizes. The NOSM research assistant would then communicate the enrolment and group assignment to [name] who will administer the AET intervention. The SC intervention will continue under the supervision of the participant's healthcare provider. Participants will be assigned a code number by the research assistant to ensure confidentiality is maintained during the transfer of data or samples between locations.

6.5 Procedures for Participant Retention

If potential PCS participants complete the intervention, they will be allowed to keep the Garmin VivoSmart HR unit. Participants in the HC group will be eligible for a \$15 gift card after completion of pre, and post assessments

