3. EXPECTED RISKS/ BENEFITS

3.1 Expected Risks

Low intensity aerobic and balance exercise poses minimal risk for healthy individuals. Like all types of exercise, there is a slight risk of sustaining a musculoskeletal injury such as a sprain or strain. There is a small risk, however, when performing aerobic and balance exercises while experiencing PCS; participants may see an increase or worsening of his/her symptoms. In order to minimize this risk, exercise will begin at a very low intensity and gradually increase. All exercise sessions will be monitored by a research team member to ensure that the session is being completed at the proper intensity. Should a participant report any PCS during a session, the session will be stopped immediately. Furthermore, to ensure that participants are healthy enough to participate in exercise, all participants will be medically cleared by [name] prior to participating in the study.

There is a minor risk that, when using the driving simulator, participants may experience symptoms such as nausea or dizziness. Breaks will be allowed during the assessment in an effort to prevent this. Water will also be readily available during the assessment should the participant require it. If a participant experiences any of these symptoms and is unable to continue, the session will end.

Physical and cognitive assessment, neuroimaging, and biomarker assessment should pose minimal risk to participants.

There is a minor social risk with respect to confidentiality. This risk will be minimized by ‘de-identifying’ the personal information with codes. All names will be removed from data/samples. All data will be stored in an encrypted file on the secure Sync.com account on a password-protected computer in a locked office at LU. Any hard copies of data such as screening checklists or the IPAQ will be coded and stored in a locked filing cabinet in a secure office at LU ([name] current office, SB 1007). All saliva samples will be coded and stored in [name] secure lab.

The results of this study will be published with aggregate data, that is, data which is combined and summarized so that no individual participant can be identified.

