4.6 Participant Withdrawal Criteria

Withdrawal will occur upon participant request. A participant who wishes to withdraw consent from the study will be asked to specify if he/she wish for any data or samples collected to be withdrawn from the study. Samples and data will be withdrawn in accordance with the participant's wishes.

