5. STUDY DESIGN

5.1 Study Design

This study is designed as a randomized controlled trial. Potential PCS participants will be referred to another member of the research team by [name]. Potential participants will then complete the informed consent process and pre screening checklist. Potential healthy participants will contact the research team directly and set up a time to complete the informed consent, pre screening process, and IPAQ. After being deemed eligible based on the screening criteria (screening checklist attached, section), PCS participants will be randomly assigned to either an AET or standard of care (SC) intervention (see section 7). Using minimization software, each intervention group will be balanced by age and sex. Healthy participants will serve as the control group (HC) and will receive no treatment. Once participants in the SC group have completed the study, the AET will be offered, although it will not be included in the data analysis. Following informed consent, PCS participants will be provided with Garmin VivoSmart HR unit to monitor aerobic activity outside of the study (accelerometer, heart rate monitor, and step counter capabilities). Participants will be required to wear the Garmin units as often as possible for the duration of the study. In place of the Garmin VivoSmart HR unit, participants in the HC group will complete the IPAQ to determine physical activity levels prior to participating in the study,.

All participants will compete a series of pre and post intervention assessments (see section 7.2) over the course of one week at Lakehead University. Following the pre intervention assessments,

participants in the AET group will complete an eight week aerobic and balance retraining program at the School of Kinesiology, Lakehead University (see section 7.2). Participants in the SC group will continue with his/her standard of care for eight weeks. Healthy participants will be instructed not to significantly change his/her lifestyle (diet, physical activity) for the duration of the study weeks. After eight weeks, all participants will complete the assessments once again.

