duration, surface, and whether the participant's eyes are open or closed. For weeks one and two participants will perform the exercises with his/her eyes open; participants will perform each exercise for 15 seconds on a firm surface in week one, and on a low density foam block in week two. In weeks three and four, participants will perform the exercises with his/her eyes closed; exercises in week three will be performed on a firm surface, while week four will be performed on a low density foam block. Duration will be increased to twenty seconds per exercise for weeks three and four. Weeks four to eight will follow the same eyes open/closed and surface progression as weeks one to four; eyes open for weeks five and six, eyes closed for weeks seven and eight. Exercises will be performed on a firm surface in weeks five and seven, and on a low density foam block in weeks six and eight. Participants will perform each exercise for 35 seconds in weeks five and six, and 40 seconds in weeks seven and eight. Following the completion of the aerobic and balance components of the session, participants will complete a cool down consisting of a series of static stretches. Each session will conclude after the completion of the cooldown.

After completion of 24 sessions (eight weeks x three-one hour sessions per week), participants will repeat the procedures for the previously described baseline assessments. Similarly, HC and SC participants will complete the baseline assessments again after eight weeks.

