| EQUIPMENT (provide justification for equipment purchases of >\$2000 in the space below) We are requesting the funds to purchase 60 VivoSmart HR Garmin units which are required for the research team to track physical activity of the participants outside of the study. These will also be used for participant reimbursement in the study. Participants that complete the study will be allowed to keep the VivoSmart. We are budgeting for an additional 20 units to account for potential loss. Each unit is \$90USD - 40% discount when ordered in bulk = \$54USD per unit x 80 units = \$4,320 x HST (13%) = \$4,881.60 USD x 1.32 (current exchange rate) = ~\$6,500. | \$ 6,500.00 | | \$ 6,500.00 |
| OTHER EXPENSES (itemize accounting services, space rental, lab service, diagnostics, patient reimbursement, etc) Publications - \$1,500 for publication page charges are requested. Conferences - We request \$1,000 for the cost of travel to conferences to present study results. Costs include conference registration, airfare, ground transportation, accommodations and food. | \$ 2,500.00 | | \$ 2,500.00 |
| Total Expenses | \$ 13,108.00 | \$ - | \$ 13,108.00 |

| Expenses Funded by Other Sources | Year 1 | Year 2 | Total |
|--|--------|--------|-------|
| SUPPLIES (itemize components below) | | | \$ - |
| EQUIPMENT (provide justification for equipment purchases of >\$2000 in the space below) | | | \$ - |
| OTHER EXPENSES (itemize accounting services, space rental, lab service, diagnostics, patient reimbursement, etc) | | | \$ - |
| | | | \$ - |
| | | | \$ - |
| Total Expenses Funded by Other Sources | \$ - | \$ - | \$ - |

| | | | |
|--|--------------|------|--------------|
| Total Budget - All Sources | \$ 50,000.00 | \$ - | \$ 50,000.00 |
| Total Budget - Innovation Fund ONLY | \$ 50,000.00 | \$ - | \$ 50,000.00 |

Notes/Budget Assumptions (Provide any additional justification to support expenditures if not referenced on P1)

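### The retention reward for concussed participants is tied to completing the intervention, not to giving the post-intervention data, and this condition bears unequally on the two randomised arms

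*Combined protocol and SAP*

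**What the plan says.** Section 5.1 gives the tracker to both randomised arms: "PCS participants will be provided with Garmin VivoSmart HR unit to monitor aerobic activity outside of the study". HC participants do not receive one.

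The documents state three different conditions for a retention reward:

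- Section 6.5, PCS participants: "If potential PCS participants complete the intervention, they will be allowed to keep the Garmin VivoSmart HR unit".
- Section 6.5, HC participants: a $15 "gift card after completion of pre, and post assessments".
- Section 16.6, budget, equipment entry: "Participants that complete the study will be allowed to keep the VivoSmart".

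Neither 6.5 nor 16.6 defines completion, sets an attendance threshold, or says what happens to the tracker of someone who stops early.

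Four other provisions bear on the point:

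- Section 7.2, on the AET programme: "After completion of 24 sessions (eight weeks x three-one hour sessions per week), participants will repeat the procedures". SC and HC participants return after eight weeks.
- Section 4.6: "Withdrawal will occur upon participant request". There is no category for stopping the sessions while staying in follow-up.
- Section 3.1, on symptoms during exercise: "Should a participant report any PCS during a session, the session will be stopped immediately".
- Section 10: for analyses of change, a participant who misses an assessment is excluded from the analysis of that assessment.

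**The concern.** A retention reward should buy the data that the analysis needs. Here that is the post-intervention assessment, because the main analysis in section 11.2 is a group-by-time interaction. The HC gift card does this. The PCS condition in section 6.5 does not: it pays for finishing the intervention, which means something different in each randomised arm.

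At stake is the completeness of the AET arm. A participant who stops the sessions early loses the device under 6.5 and has no stated reward for coming back. No section says that this participant is still assessed, and section 10 drops the change data if no post value exists. If those who stop early tend to have done worse, the remaining AET participants give too favourable a picture.

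**Working it through.** The plan gives no figure for this point, so the check is mainly a comparison of the provisions. Two small calculations follow.

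**1. What the 6.5 condition asks of each arm, read literally**

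| | AET | SC | HC |
|---|---|---|---|
| Intervention | 8 weeks x 3 = 24 supervised sessions (7.2) | Usual care continuing for eight weeks (5.4) | None |
| Reward condition | Complete the intervention | Complete the intervention | Complete pre and post assessments |
| Can fail the condition by stopping early? | Yes | Hardly; there are no study sessions to miss | Not applicable |
| Reward depends on the post assessment? | No | No | Yes |

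The condition is therefore unequal between AET and SC, and in neither arm does it depend on returning. An AET participant who finishes the sessions has earned the device before the post assessments, and so has an SC participant who has continued usual care.

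**2. What happens to an AET participant who stops early**

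- 6.5: the condition is not met, so the device is not kept.
- 16.6: the outcome depends on whether completing the study includes completing the sessions, which is not stated.
- 7.2: the AET post assessment is described as following 24 sessions. Section 5.1 says more generally that all participants are reassessed after eight weeks. Neither section addresses early stopping.
- 10: without a post value, the participant is excluded from that analysis of change.

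**3. Value of the device**

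The budget inputs are US$54 per unit after discount, 13% tax and an exchange rate of 1.32.

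54 x 1.13 x 1.32 = CAD 80.5 per unit. For 80 units, 80 x 80.5464 = CAD 6,444, which agrees with the budgeted figure of about $6,500.

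The HC card is $15, so the tracker is worth 80.5 / 15 = 5.4 times as much if the card is in Canadian dollars.

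**4. What losing early stoppers could do (assumed values)**

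Suppose that k of 20 AET participants stop after worsening by 0.5 SD, and the other 20 - k improve by 0.5 SD. The mean change in all 20 is 0.5 - k/20. If none of the k returns, the observed mean is 0.5. The overstatement is k/20 SD.

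| k | Mean in all 20 | Mean in returners | Overstatement |
|---|---|---|---|
| 1 | 0.45 | 0.50 | 0.05 |
| 3 | 0.35 | 0.50 | 0.15 |
| 4 | 0.30 | 0.50 | 0.20 |

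This is the effect of complete-case exclusion when every stopper is lost. It is not the effect of the tracker rule. Only the additional non-return caused by losing the device belongs to the rule. The documents give nothing from which to estimate that number, and it could be zero.

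**The case against.** **A reader might infer that the rule pays AET participants to conceal symptoms.** The documents do not establish this. Section 3.1 says that a symptom report stops the session. It does not say that the report ends the intervention, that a stopped session fails to count, or that the device must be returned. Self-report is also not the only safeguard. Sections 3.1 and 7.2 provide medical clearance, a low starting intensity with gradual increase, a certified supervisor, and heart-rate monitoring. What stands is narrower: because completion is undefined, participants cannot tell whether stopped or missed sessions count against them. A disincentive to report or stop is therefore plausible.

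**A reader might also infer that SC participants keep an incentive to return that AET stoppers lose, so that loss is one-sided because of the tracker.** This does not follow. If SC participants qualify simply by continuing usual care, the tracker gives them no reason to return either. If completion is instead taken to include the post assessments, SC participants no longer qualify automatically. The two readings cannot be combined. SC participants do have a separate reason to stay, since AET is offered once they have completed the study (5.1, 12.3), but that does not come from the tracker.

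**Other points on the sponsor's side.** The budget is a funding form and is weak evidence of the operating rule. The consent pages are not available and may say what happens to the device. Section 5.1 can be read as bringing early stoppers back at eight weeks. A reward for finishing the sessions also supports adherence, which is a legitimate aim. These points lower the weight of the concern. They do not remove the mismatch between 6.5 and 16.6, or the fact that 6.5 does not reward the post assessment.

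**Conclusion.** The point holds as a cheap improvement to the retention rule, not as a demonstrated bias or safety failure.

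Established from the text: the PCS reward in 6.5 depends on the intervention while the HC reward depends on the assessments; the budget words the tracker condition differently; the 6.5 condition bears unequally on AET and SC; and, read literally, an AET participant who stops early loses the device and has no stated reward for returning.

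Conditional: early AET stoppers can drop out of the comparison through sections 7.2 and 10. The result favours AET only if they did worse than those who stayed. The 0.05 to 0.20 SD range rests on assumed values and describes complete-case loss in general. No size can be assigned to the tracker rule itself.

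**What to change.** 1. In section 6.5, let PCS participants in both arms keep the device after attending the post-intervention assessments, whether or not all AET sessions were completed. This matches the HC condition.
2. Reconcile 6.5 with the budget wording in 16.6, so that one defined condition applies.
3. In section 7.2, state that AET participants who stop the sessions early are still invited to the eight-week assessments. Without this, the new condition in 6.5 would refer to a visit that 7.2 does not describe for them.
4. Tell participants that reporting symptoms, or missing or stopping sessions, does not affect whether they keep the device. Check the consent wording for consistency.

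**Cost.** A sentence or two in each of 6.5 and 7.2, plus any matching consent text. No further purchase is needed: the budget covers 80 units, and only the 40 PCS participants receive one, which leaves 80 - 40 = 40 spare. A few devices would go to participants who did not finish AET, additional early stoppers may attend the post assessments, and the incentive to finish all 24 sessions becomes slightly weaker.

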7. STUDY PROCEDURES

7.1 Time and Events Schedule

| Event/Activity/Procedure | Medical appointment | Informed Consent Visit | Pre-intervention assessment A (LU) | Pre-intervention assessment B (LU) | Pre-intervention assessment C (LU) | Pre-intervention assessment D (LU) | AET (3x week)/SC/HC | Post-intervention assessment (A, B, C, D) |
|--------------------------|---------------------|------------------------|------------------------------------|------------------------------------|------------------------------------|------------------------------------|---------------------|---|
| Referral | X | | | | | | | |
| Informed Consent | | X | | | | | | |
| Screening | | X | | | | | | |
| ImPACT | | | X | | | | | X |
| BESS | | | X | | | | | X |
| Saliva | | | | X | | | | X |
| Oddball and Flanker task | | | | | X | | | X |
| Driving Simulation | | | | | | X | | X |
| Intervention | | | | | | | X | |

7.2 Description of Study Procedures, Assessments and Participant Activities

Once participants have been randomized into groups, participants will be scheduled to complete the pre intervention assessments at Lakehead University over a period of one week. These assessments will include a physical, cognitive, neuroimaging, biomarker, and driving behaviour assessment. These assessments will also be completed after the intervention in PCS participants, and after eight weeks in HC.

Physical and Cognitive Assessment:

Participants will complete the Immediate Post-Concussion Assessment and Cognitive Testing (ImPACT) at the School of Kinesiology, Sanders building, Lakehead University. The ImPACT will be used as a standard measure of cognitive abilities including: attention, working memory, processing speed, and reaction time. At a mutually agreed upon date and time, participants will meet a member of the research team at the Lakehead University Sanders Fieldhouse. Before beginning the assessments, a member of the research team will verbally restate the participant's rights and confirm that he/she is still willing to participate in the study.

Participants will then be set up at a computer station, where they will follow the on screen instructions for completing the ImPACT battery. Following completion of the ImPACT battery, participants will be asked to stand in a variety of static positions including: narrow based double leg stance, single leg stance, and tandem stance with one foot behind the other. Participants will perform each stance position with his/her eyes open and closed and on a firm and soft surface using the Balance Error Scoring System (BESS) protocol. Each stance will be performed over an AMTI force platform. This approach will be used to measure participant sway, centre of pressure displacement, and to count for the number of perturbation errors induced during the balance test³⁴. The session should last approximately one hour.

Biomarker Assessment:

Brain-derived neurotrophic factor (BDNF) will be assessed using a morning saliva sample. Participants will be asked to refrain from brushing his/her teeth, smoking, and consuming food or drink within two hours of the sample collection. Participants will also be asked to avoid alcohol consumption 12 hours prior to sampling. At a mutually agreed upon date and time, the participant will meet a member of the research team at the Sanders building, Lakehead University. Before beginning saliva collection, the member of the research team will verbally restate the participant's rights and confirm that he/she is still willing to participate in the study. Saliva will then be collected from participants in room SB-1025 (biohazard containment level 1) via the passive drool method into a tube, which will then be put on ice and transported to [name] lab for processing. Processed saliva samples will be stored until samples have been collected from all participants. If the sample is collected immediately prior to the physical and cognitive assessments, participants will be provided with light refreshments after saliva has been collected.

To analyze salivary samples for BDNF, a sandwich ELISA technique will be used (Mandel, Ozdener, & Utermohlen, 2011). A 96-well microtiter plate (Nunc Maxisorp; VWR, West Chester, PA) will be incubated overnight at four degrees Celsius. In the 96-well plate, a total of 100 µl of monoclonal mouse anti-human BDNF (clone 35928.11; Millipore, Etobicoke, ON) will be diluted to 1 µg/ml in a filter-sterilized phosphate buffered saline (PBS) at a pH of 7.4. The plate will be washed three times, soaking for one minute between washes. It will be washed with tris-buffered saline (TBS) plus 5% tween (TBST), and blocked with 300 µl of 3% bovine serum albumin (BSA) in 0.05% PBST for two and a half hours at room temperature. Samples will then be acidified for 20 minutes to a pH of 3.0 using 1M of HCl. Samples will be neutralized after 20 minutes using 1M NaOH diluted in a 1% BSA buffer in PBST to a ratio of 1:4. Comparison will be made between samples and standards diluted in the same buffer as the samples. These will range from 15.63 to 500 pg/ml using a full-length, homodimeric recombinant BDNF (Peprotech, Rocky Hill, NJ). The plate will then be washed five times, before adding in duplicate 100 µl of sample/standard. At room temperature, the plate will then be incubated at room for two hours with agitation, before being washed five more times. After being washed again, a total of 100 µl of polyclonal chicken anti-human BDNF (2.5 µg/ml;

Promega, Madison, WI) will be added to the plate. After two and a half hours, the plate will be washed five times again. Following this incubation, 100 µl of anti-chicken IgY-HRP (1 µg/ml; Promega) will be added to each well, before being incubated for one hours. The pate will be washed five times after this incubation. A total of 100 µl of room temperature Pierce 1-Step Ultra TMB solution (Pierce Biotechnology, Rockford, IL) will then be added to each well for fifteen minutes. To stop the reaction at fifteen minutes, 100 µl 1M HCl will be added to each well to stop the reaction. The assay will be read at 450 nanometres (nm). Total BDNF (pg/ml) will be calculated by using the standard regression equation provided with the standards. To the research team's knowledge, BDNF is not used as a diagnostic tool, thus no incidental findings are expected.

Neuroimaging:

Neural processing will be assessed by using continuously recorded EEG during the performance of computer based tasks commonly used in experimental psychology for assessing divided attention and inhibitory control. At a mutually agreed upon date and time, participants will meet a member of the research team at the Sander building, Lakehead University. A member of the research team will then escort he/she to [name] Vision Laboratory at Lakehead University. Before beginning the procedures, the member of the research team will verbally restate the participant's rights and confirm that he/she is still willing to participate in the study. Participants will be seated at a desk and fitted with an EEG cap and 32 channels will be prepared with gel. Once all recording sites are ready for recording the participant will be familiarized with the task procedures and equipment. At the desk he/she is seated at, he/she will view a monitor and be provided with a response pad. The order of the tasks presented will be counter-balanced in order to reduce the chance of order effects. Participants will be offered opportunities for breaks in between blocks of each task as well as in between the start of tasks. Event related potential (ER) will be measured for the duration of the tasks. Completion of the session should require two hours.

ODDBALL paradigm:

The Oddball paradigm is a commonly used task to test attention by requiring participants to make a specific response to rare target stimuli amongst more repetitive, distractor stimuli³⁵. In this visual version, participants will be provided an instruction at the outset of a block that indicates what the target stimulus for that block will be. During each trial, a stimulus (shape/letter) will be displayed for 200 milliseconds (ms). Participants will be instructed to respond to each stimulus as quickly and accurately as possible with a button press of one of two buttons; a button to denote distractor stimuli, and a button to indicate target stimuli. The interstimulus interval will be variable (1400-1600 ms) to reduce anticipation. Participants will complete 400 trials separated into 5 blocks with an option for rests between each block.

FLANKER task:

The Flanker task is commonly used to test the ability to attend to central relevant information (the direction of an arrow) while disregarding irrelevant distracting stimuli (pairs of flanking arrows presented on either side of the central arrow). To identify the direction of the central arrow, participants will press a left or right button to indicate the direction of the central arrow. Data will be separated into time frames containing the components of interest (the N200 and P300). The session is concluded after completion of the oddball and flanker tests twice.

Behaviour Measure (Driving Simulator):

The performance of participants in a driving simulator will be assessed by measuring his/her reaction time and counting the number of passes and failures when anticipating potentially dangerous traffic situations. Reaction time will also be measured during dual-tasking activities. At a mutually agreed upon date and time, the participant will meet a member of the research team at the Sanders building, Lakehead University. A member of the research team will then escort he/she to the Centre for Research on Safe Driving (Braun Building, room 1024). Before beginning the assessment, the member of the research team will verbally restate the participant's rights and confirm that he/she is still willing to participate in the study. Participants will then be fitted with a POLAR SP0810 heart rate monitor before being introduced to the STISIM Drive[®] Model 400 driving simulator. Participants will be seated approximately 70% of his/her arm's length from the steering wheel with a backrest inclination of 10° (Majid et al., 2013; Yoo, An, Lee, & Choi, 2013)^{36,37}. The simulator will be connected to a PowerLab (16/30) data acquisition unit which will be interfaced with LabChart 7 software. Heart rate (HR), heart rate variability (HRV), and reaction time (RT) will be measured using LabChart 7.

Participants will perform a 10 minute orientation drive to familiarized his/herself with the control and feel of the driving simulator. During the orientation drive, he/she will be exposed to examples of the dual tasking activities so that he/she will know how to successfully respond to the prompts. Once a participant feels comfortable with the simulator, the 20 minute simulation and data collection will begin. The simulation will be based on the Thunder Bay road system with traffic and pedestrians present. Weather will be clear and visibility will not be reduced. Reaction times will be measured during predetermined scenarios and will be recorded from the moment stimulus occurs to the moment the brake is depressed or evasive maneuver performed. Heart rate and HRV will be recorded throughout the duration of the simulation and will be marked at the beginning and end of each dual task scenario and reaction time activity. Participants will be exposed to several scenarios. These scenarios include: Vehicle incursion at intersection, pedestrian incursion from side of the road, sudden braking by a vehicle in front of participant, pedestrian incursion in school zone, braking by a vehicle in front of participant, and animal incursion (attached)

During dual task events, red triangles will be displayed over either of the side mirrors. These triangles will be deactivated by the press of a button on either side of the steering column, accounting for the dual tasking component of the reaction time scenarios. These scenarios will

have a three second threshold for time to react before the scenario will be considered a fail (National Safety Council, 2012; Triggs & Harris, 1982)^{38,39}.

In the event a participant is unsuccessful during a dual tasking scenario and collides with on screen stimuli, he/she will continue with the simulation with no second chance at completing that specific activity. If a participant begins to experience symptoms of simulator sickness, the scenario will be paused to allow him or her to take a break from the screen and/or have something to drink or eat. The research team member will have water on hand, if required by the participant. When he/she feels ready to proceed, the simulation will be resumed from the point of the original pause. If a participant feels that he/she is unable to continue, the simulation will be stopped and data collection terminated.

Aerobic and Balance Retraining Program:

After completing baseline assessments, PCS participants assigned to the AET intervention will complete an eight week supervised AET program. The program will consist of three sessions per week, approximately 40-60 minutes each. Each session will be completed under the supervision of a trainer with the Canadian Society for Exercise Physiology (CSEP-CPT) certification. At mutually agreed upon dates and times, participants will meet a member of the research team at the Sanders building, room SB-1025. Before beginning the intervention, the member of the research team will verbally restate the participant's rights and confirm that he/she is still willing to participate in the study. Participants will then be outfitted with a Polar F2 heart rate monitor, in order monitor exercise intensity during the session. Exercise intensity for each session will be based on the participant's heart rate reserve (HRR). At the first session, the participants HRR will be calculated using the Karvonen formula; Target Exercise Heart Rate = $((220 - \text{Age} - \text{Resting Heart Rate}) \times \% \text{Intensity}) + \text{Resting Heart Rate}$. Once the participant's HRR has been calculated, the participant will begin the aerobic component of the session.

The aerobic component of the session will be performed on a cycle ergometer. Participants will begin with a five minute warmup at a self selected speed, which will be used to bring the participant's heart rate to the desired intensity. Intensity for each session will start at 20% of HRR, and increase linearly by 10% for the first four weeks; at week four, participants will be cycling at an intensity of 50%. Weeks five and six will be performed at 55% of HRR, week seven will be performed at 60% of HRR, and week eight will be performed at 65% of HRR. Duration will follow a similar pattern for weeks one to four, beginning at 20 minutes and increasing in five minutes/week increments. At week five, duration will be reduced to 25 minutes, and then increase to 30 minutes for weeks six to eight.

Following completion of the aerobic portion of the session, participants will rest for five minutes before beginning the balance component of the session. Participants will perform three balance exercises (in order) each session: narrow based double leg stance, single leg stance, and tandem stance. Difficulty of these exercises will be progressively increased by modifying the

duration, surface, and whether the participant's eyes are open or closed. For weeks one and two participants will perform the exercises with his/her eyes open; participants will perform each exercise for 15 seconds on a firm surface in week one, and on a low density foam block in week two. In weeks three and four, participants will perform the exercises with his/her eyes closed; exercises in week three will be performed on a firm surface, while week four will be performed on a low density foam block. Duration will be increased to twenty seconds per exercise for weeks three and four. Weeks four to eight will follow the same eyes open/closed and surface progression as weeks one to four; eyes open for weeks five and six, eyes closed for weeks seven and eight. Exercises will be performed on a firm surface in weeks five and seven, and on a low density foam block in weeks six and eight. Participants will perform each exercise for 35 seconds in weeks five and six, and 40 seconds in weeks seven and eight. Following the completion of the aerobic and balance components of the session, participants will complete a cool down consisting of a series of static stretches. Each session will conclude after the completion of the cooldown.

After completion of 24 sessions (eight weeks x three-one hour sessions per week), participants will repeat the procedures for the previously described baseline assessments. Similarly, HC and SC participants will complete the baseline assessments again after eight weeks.

